University of Chicago will provide pre-programmed tablets to all study sites. These tablets have been programmed by the Research Computing Group within the Department of Public Health Sciences (leadership [name]) at the University of Chicago to ensure data protection and enable data transfer. All data collection will be conducted electronically via tablets and data will be uploaded into databases hosted by University of Chicago. These are similar procedures as have been developed with [name] for NIDA's Methodology and Advanced Analytics Research Center (PI [name]).

The University of Chicago BSD IRB will act as IRB of Record for all sites, except Indiana University (due to their enrollment of juvenile CJI populations) who will use their own institutional IRB.

METHODS

AIM: Test intervention efficacy (numbers tested – COVID-19 test results will be collected as study data; numbers vaccinated – COVID-19 vaccine records will be collected as part of the study) and community factors that may moderate efficacy. Secondary analysis to compare numbers tested in SNS strategies and COVID-19 contact and determine whether COVID-19 status within social networks impacts the referral process.

We hypothesize that participants randomized to receive SNS+ (SNS+COVID-19 messaging) will be more likely to have their network members successfully tested and vaccinated (study participants will be given COVID-19 vaccine information and contact information to vaccination sites in their community. Vaccination will depend on the network members' tier/health department eligibility for vaccination). We also hypothesize that both SNS and SNS+ will generate more people tested per index as compared to COVID-19 contact tracing. Finally, we anticipate that there may be differential intervention effects across sites, by CJI status, prior COVID-19 testing history, race/ethnicity, and network composition, and will formally evaluate these differences as part of analyses.

Recruitment of Index and Network Member study participants.

We will enroll index seeds (12% of sample) ages 18 and over who are CJI or low-income Latinx across eight collaborative sites. Index clients and their social network referrals will be recruited by local Research Assistants (RAs) embedded within community-based agencies and community health care settings that provide a number of in person and remote social and care services, including community COVID-19 testing.

Recruitment activities may include:

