- (1) 18 years or older;
- (2) spend majority of their time in the metropolitan area or county where recruited;
- (3) have access to a phone for 21-day follow-up call; and
- (4) primary communication in English or Spanish (based on site chart above) AND at least one of the following:
 - (i) ever had CJI (operationalized as any jail, prison, arrest, parole (completed), probation, drug court);
 - (ii) ever had negative interaction with police or law enforcement that did not lead to an arrest or jail/prison time (operationalized as ever stopped, searched, physically or verbally abused, or had another negative interaction with police or law enforcement);
 - (iii) ever witnessed a negative interaction with police or law enforcement (operationalized as ever witnessed another person being stopped, searched, or physically or verbally abused by police or law enforcement);
 - (iv) lower-income Latinx (operationalized as at or below 250% of FPL).

Social network referrals will be:

- (1) linked to the index as a “friend, family, coworker or someone you spend time with on a regular basis”;
- (2) visit within two weeks of index visit;
- (3) 18 years or older;
- (4) spend the majority of their time in the metropolitan area or county where recruited;
- (5) have access to a phone for 21-day follow-up call; and
- (6) primary communication in English or Spanish (based on site chart above).

[figure not shown]
Exclusion criteria include:

- (1) inability to provide informed consent; and
- (2) active COVID-19 symptoms per CDC. Participants with COVID-19 symptoms will be referred for free testing at existing partners for each of the study sites.
- (3) currently on parole

Study Visit Procedures

All study participants (index and referral) will go through the following study procedures (Figure 4) include:

- Informed consent;
- Day 1 survey;
- Randomization;
- Messaging intervention (for SNS+ only);
- COVID-19 testing
- Social Network referral
- Day 21 Follow-up

1. **Informed Consent.** Eligible participants will be asked to participate in written informed consent using either a paper consent or electronic consent. The following consent processes applies to both the study consent form and the release of information form.

Paper Consent in-person:

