- 1) Visually display a driver's license or state ID

- 2) Visually display an alternative photo ID (employee ID, school ID, etc) in combination with a piece of mail displaying the subject's name.
- 3) Visually display an alternative photo ID (employee ID, school ID, etc) alone
- 4) Visually display one of the following pieces of mail with subject's name and address: utility bill, cellphone bill, correspondence from the secretary of state or other government organization
- 5) Visually displaying any piece of mail listing the subject's name and address
- 6) Asking the subject to verbally state their name

2. **Day 1 Survey.** Following consent, study participants will complete an electronic survey that includes social network inventory. Identifying information of social network members (first name and last initial and cross streets/zipcode/neighborhood) is collected through self-report for the purposes of connecting social networks of study subjects. Day 1 Survey is found in Appendix B. This will survey will be completed on the day of recruitment and will take 60 minutes. The RA can interview participants who have difficulty self-administering the survey.
3. **Randomization.** Will occur following the survey, and participants in the SNS+messaging arm will receive the messaging intervention (discussion tools and coaching). Study participants will be randomized to receive no messaging (i.e., SNS only) or SNS+messaging with equal probability. Randomization will be performed at the participant level, meaning that in general, participants within a recruitment cluster will be assigned to different groups. Random assignments will be provided by the University of Chicago via a web-based API, with the touchpads programmed to retrieve an assignment at the appropriate time and deliver the messaging (or not), as appropriate.

Indexes and first-degree referrals will be randomized as described above. Second-degree referrals will also be randomized, however, we will not ask for additional SNS referrals from them if the study sample size has been reached.

4. **Messaging Intervention.** Study staff will be notified of group allocation and provide the in-person message reinforcement and will address questions related to messaging.

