 - a. ***C3 Study Conditions.*** Trained community engagement coordinators (CEC) that exist across C3 sites will deliver the study conditions. The CECs will have capacity to support multiple participants simultaneously in the self-administered portion of the study visit: clarifying any survey items, troubleshooting any technology/data collection issues, and transitioning to interviewer administered for people with limited literacy. CECs will provide the appropriate scripted messaging strategy based upon condition assignment (see conditions below) and will follow with describing and motivating the SNS network referral process.
 - b. ***SNS Study Condition.*** Study participants in the SNS condition will receive the SNS intervention training which will take about 30 minutes. This will occur towards the end of the study visit when CEC staff describe the SNS, construct a plan for successfully referring network members into the study, and discuss compensation for the recruitment efforts. CECs will specifically discuss network members of interest: "friend, family, coworker or someone you spend time with on a regular basis". Walkthrough and scenario play will be strategies to assist with planning regarding: (1) how the conversation will be raised, (2) how potential barriers to testing will be addressed, (3) how the screening by phone or web survey will be conducted, (4) what information about the study will be shared. Information from the client providing referrals will be kept confidential. Participants will be compensated \$20 per successful test completed per network member and up to six referrals, consistent with our previous work.⁴²
 - c. ***SNS+Messaging Condition.*** The SNS+ condition will include everything described in the SNS condition above. In addition, a scripted message (Appendix C) in the participant's preferred language

will be deployed via the tablet in written or audio format. Training for this additional messaging will take about 15 minutes.

- d. *Quality Monitoring* - A sample (5%) of the trainings will be recorded (video and/or audio) for quality improvement purposes. These recordings may be shared amongst the respective sites-specific study team (not shared outside of the subject's study site). Subjects will be asked whether they are willing to have the session recorded and can indicate yes or no on the study consent form.

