- 5. **COVID-19 Testing**. All study participants, irrespective of symptoms, will be tested for COVID-19. Based on routine practices of the site, testing will be either administered by a clinical professional or conducted through self-administration according to CDC guidelines (Appendix I). Testing procedures will follow existing SOPs utilized at each site, utilizing FDA-approved tests. COVID testing at these sites is covered by public health programs for each site.

Test result provision will be provided by the testing/clinical team. All subjects will be provided with the CDC's information page "What Your Test Results Mean" (Appendix J).

- 6. **COVID-19 Vaccination**: All subjects will be provided with the link to CDC's COVID-19 vaccine information page "Key Things You Need To Know About COVID-19 Vaccines" (Appendix K) and a link to CDC's "Vaccines for COVID-19" page available at <https://www.cdc.gov/coronavirus/2019-ncov/vaccines/index.html>. Access to vaccines will follow routine practices and will depend on a participants' tier/health department eligibility to get the vaccine as well as vaccine availability. Contact information for vaccination sites and any referrals will be given according to the normal practices at each site.

All participants will be asked sign release of information forms for study team members to obtain test results and vaccination records. Vaccination records will also be collected through participant self-report (participants can show study staff their vaccination card). COVID test results and vaccine records will be collected as part of study data and will be needed to determine the effectiveness of the intervention.

- 7. **Social Network Referral** – Network referrals will be conducted as outlined above (See SNS Study condition). A study information card (Appendix D) will be given to all enrolled subjects to share with their network referrals. The information card contains information about the study and study team contact information. Linkages between study participants are collected through a code/code word process that our team has used in previous network referral studies.

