Primary outcome analysis (overall comparison of SNS vs. SNS + messaging). The primary outcome analysis will compare the likelihood of testing among network members and the total number of referrals tested between those assigned to SNS and those assigned to SNS plus messaging. Our initial analysis will not adjust for covariates, relying instead on the randomization to justify the comparison. We shall then incorporate covariates—measured at both the level of the network member (e.g., member characteristics and the nature of the relationship to the participant) and of the participant—to improve the precision of our estimates and to identify demographic and social characteristics associated with differences in referral yield. In addition, we shall consider interactions between intervention group (SNS vs. SNS + messaging) and participant characteristics to determine whether messaging is more effective in certain groups than others. Since we shall consider several possible interactions, we shall use partial pooling within a Bayesian estimation framework⁴⁶ to avoid bias and address the issue of multiple comparisons.

We will compare the probability of participants being vaccinated in the SNS vs. SNS + messaging arm using logistic regression with each participant treated as an observation (vaccinated vs. not). This will be modeled with a three-level hierarchical model with random effects at the level of the recruitment cluster and study site. We will also consider adjustments for time trends in vaccine availability and participant eligibility.

Secondary outcome analyses: We shall use negative binomial regression to compare the average number of referrals tested per index client between those recruited to C3 and assigned to the SNS condition and a comparison group of clients at the same sites receiving standard contact tracing only. This analysis will be performed first using only those contact tracing clients who visited the sites on a day randomized to no C3 recruitment, since these individuals should, on average, be similar to those recruited into the study. A subsequent analysis will be performed using a larger set of non-study clients to increase precision; this will use covariates capturing demographic and other client characteristics to adjust for potential differences between the C3 SNS group and the non-study comparison group. Analyses will use generalized linear mixed models similar to those described above, as appropriate.

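### The vaccination hypothesis is about network members by recruiter's arm, but the planned analysis compares participants' own vaccination by own arm and has no start date separating new from prior vaccination

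*Combined protocol and SAP*

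**What the plan says.** **Hypothesis.** The Methods aim expects that participants randomized to SNS+ "will be more likely to have their network members successfully tested and vaccinated". The exposure is the recruiter's arm; the outcome belongs to the network member.

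**Outcome and analysis.** Primary Outcomes, item 3, counts study participants who become vaccinated by way of the network strategy. The Primary outcome analysis section compares the arms by "logistic regression with each participant treated as an observation (vaccinated vs. not"), with random effects for recruitment cluster and site. It has no term for the recruiter's arm. Adjustment for vaccine availability over time and for eligibility is optional. For testing, by contrast, the Analytic overview models each network member as an observation nested within the recruiting participant.

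**Randomization.** Study Visit Procedures, item 3: "Randomization will be performed at the participant level, meaning that in general, participants within a recruitment cluster will be assigned to different groups".

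**Exposure.** Item 4c: "The SNS+ condition will include everything described in the SNS condition above. In addition, a scripted message (Appendix C"). The message goes to the randomized person directly.

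**Who is analysed.** The list headed "Exclusion criteria include" has three entries (inability to consent, active symptoms, current parole). Prior vaccination is not one of them. Attrition and missing data puts everyone enrolled into the analyses.

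**Data.** Item 6 provides for "release of information forms for study team members to obtain test results and vaccination records", plus self-report or a vaccination card. No start date, window or dose rule is attached to the outcome.

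**The concern.** There are two separate problems.

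1. The hypothesis and the analysis ask different questions. A referral's own arm is independent of the recruiter's, so any benefit that reaches a referral only through a recruiter who received the messaging falls equally on both own-arm groups. A null own-arm result would not refute the stated hypothesis, and a positive one would not confirm it.

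2. The analysis text scores people as vaccinated or not, among all enrolled, with no start date. Vaccines were already being distributed when the protocol was written (Background), so some entrants are likely to be vaccinated already. If they score as successes they carry no information on the intervention, pull the odds ratio towards 1 and cost power in a comparison listed as primary. If they do not, the plan should say so, or the choice will be made later, possibly with data in hand.

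**Working it through.** The documents state no vaccination rate, effect size or power, so there is no plan figure to reproduce. The stated 87% power concerns testing. All vaccination rates below are assumptions.

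**1. Own arm against recruiter's arm**

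Let A be a referral's own arm and R the recruiter's arm, each 1:1 and independent. With uptake = base + d·A + r·R, the expected own-arm difference among referrals is d and the expected recruiter-arm difference is r. If d = 0, the own-arm difference has expectation 0 whatever r is.

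Simulation inputs:
- From the protocol: 300 seeds, 2,100 referrals, individual 1:1 randomization.
- Assumed: base uptake 10%, nobody vaccinated at entry, independent outcomes.
- Referral tree: x + x² = 2,100/300 = 7, so x = 2.19. This gives 657 first-degree and 1,443 second-degree referrals.
- 3,000 runs, two-sided 0.05.

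| Assumed effect | Own-arm difference, rejection | Recruiter-arm difference, rejection |
|---|---|---|
| 4 points through recruiter only | 0.0 points, 4.9% | 4.0 points, 80.5% |
| 2 direct + 2 through recruiter | 2.0 points, 34% | 2.0 points, 29% |
| 4 points direct only | 4.0 points, 86% | 0.0 points, 5.6% |

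A separate simulation with a recruiter-only effect of 20% vs 26% gave the same pattern: 0.0 points and 4.6% by own arm, 6.0 points and 90% by recruiter's arm.

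The 80.5% is a best case. With 20% vaccinated at entry, 1,050 × 0.8 = 840 referrals per arm remain and power is 0.71 if they are independent. The plan's within-network ICC of 0.46 is for testing; borrowing it for vaccination lowers this further. For equal counts, the Power calculations networks and Poisson counts, a referral shares its recruiter with on average 1.19, 1.73 or 2.19 others. Thinning these by 0.8:
- 1 + 0.8 × 1.19 × 0.46 = 1.44, power 0.56
- 1 + 0.8 × 1.73 × 0.46 = 1.64, power 0.51
- 1 + 0.8 × 2.19 × 0.46 = 1.81, power 0.47

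The middle variant is approximate, because those networks average 1.70 referrals rather than 2.19.

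**2. Prior vaccination scored as an outcome**

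Let b be the share vaccinated at entry and p₀, p₁ the uptake among the rest.
- Scored literally, each arm's rate is b + (1 − b)p, so the difference is (1 − b)(p₁ − p₀), with 1,200 per arm.
- Restricted to those unvaccinated at Day 1, the difference is p₁ − p₀, with 1,200(1 − b) per arm.
- Power = Φ(difference/SE − 1.96), where SE² = [π₀(1 − π₀) + π₁(1 − π₁)]/n and π₀, π₁ are the arm rates. No clustering.

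With p₀ = 0.10 and p₁ = 0.14:

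| b | Literal rates | Difference | Power, literal | Power, unvaccinated only |
|---|---|---|---|---|
| 0 | 0.100 vs 0.140 | 0.040 | 0.86 | 0.86 |
| 0.1 | 0.190 vs 0.226 | 0.036 | 0.59 | 0.82 |
| 0.2 | 0.280 vs 0.312 | 0.032 | 0.40 | 0.77 |
| 0.4 | 0.460 vs 0.484 | 0.024 | 0.22 | 0.65 |
| 0.6 | 0.640 vs 0.656 | 0.016 | 0.13 | 0.48 |

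At b = 0.4, literally: SE = √[(0.46 × 0.54 + 0.484 × 0.516)/1,200] = 0.0204; 0.024/0.0204 = 1.18; Φ(1.18 − 1.96) = 0.22. The odds ratio is 1.10, against 1.47 among the unvaccinated. Restriction also loses power as b rises, but far less.

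**The case against.** The best defence is that the plan is consistent where it counts. Primary Outcomes item 3 is defined on study participants and the analysis matches it. The aim's own parenthetical describes giving vaccine information directly to participants. On that view one loosely worded hypothesis is the outlier. This largely stands: the own-arm question is legitimate and should be kept, and rewording the aim is a sufficient remedy.

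On the second problem, item 3 ties vaccination to the network strategy and to people given vaccine information, which points to new vaccinations. That also stands. But the analysis section does not repeat the limit and neither place gives a start date. The optional time-trend and eligibility adjustments do not remove prior vaccinations.

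A reader might infer more than the documents support:
- *That network members' vaccination goes unanalysed.* Referrals are an estimated 2,100 of the 2,400 participants and are in the model. Only the recruiter-arm contrast is missing.
- *That the plan intends to count prior vaccinations.* That is the literal reading of one section and the less natural reading of the whole.
- *That the comparison is biased towards one arm or has an inflated false-positive rate.* Individual 1:1 randomization balances prior vaccination in expectation.
- *That baseline vaccination status is not collected.* The survey appendices are not shown, so this cannot be judged.

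**Conclusion.** The concern holds in two limited parts, and both should be fixed.

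First, the planned vaccination analysis measures the direct effect of messaging on the person who receives it. It cannot test an effect acting through the recruiter, which is what the stated hypothesis describes. This follows from individual randomization and needs no assumed rates. Only the illustrative rejection rates do.

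Second, the vaccination outcome lacks a start date, window and dose definition. If the analysis text is followed literally, the risk difference shrinks by the factor 1 − b. That factor is exact when uptake applies only to those unvaccinated at entry. The power loss rests on assumed uptake of 10% vs 14%, an assumed entry share and no clustering. Other uptake rates would change the figures but not the direction.

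**What to change.** **Hypothesis and analysis.** Choose one:
- Reword the vaccination part of the Methods aim to the own-arm question. This is the cheapest option and costs one sentence.
- Keep the own-arm analysis and add a secondary recruiter-arm analysis. The outcome is the number of referred members who enrol and are newly vaccinated, per randomized participant asked to refer (zero if none). Use negative binomial regression with cluster-robust variance, as the Analytic overview does for referrals.

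The second option needs two details. Record who was asked to refer, since for second-degree participants "we will not ask for additional SNS referrals from them if the study sample size has been reached". Date new vaccinations from the recruiter's randomization. Because referrals must "visit within two weeks of index visit", this can precede the referral's own Day 1.

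Its downside is that the count mixes referral yield with uptake and has limited power. A simulation with 300 + 657 = 957 recruiters and 20% vaccinated at entry used uptake ICC 0 or 0.46, the latter borrowed from testing. Uptake of 10% vs 14% alone (ratio 1.40) was detected in 50% or 33% of runs. Yield of 0.44 vs 0.52 alone (ratio 1.18) rejected in 17% or 12%. A positive count would therefore not by itself show higher uptake per referral.

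**Outcome definition.** In Primary Outcomes and Primary outcome analysis:
- count only vaccinations dated after randomization, within a stated window;
- define vaccinated as first dose or completed series, so that people partly vaccinated at Day 1 can be classified;
- restrict this analysis to participants not vaccinated at Day 1, and state it as an exception to the rule that all enrolled are analysed.

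Keeping everyone and adjusting for Day 1 status is not a good substitute. Already vaccinated people cannot have the outcome, so the logistic model separates on that covariate and may not converge.

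The cost is text, plus one modest analysis if the second option is chosen. First confirm that Day 1 status and vaccination dates are captured.

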The Social Network Strategy (SNS) was developed for HIV and is adapted to accelerate COVID-19 testing to identify networks most at risk. Social network interventions are recognized as highly potent testing interventions that move beyond individual-level "risk"³⁶ which are key to COVID-19 elimination efforts. Network mobilization/induction is a Type III intervention strategy that stimulates peer-to-peer interaction to create behavioral diffusion through existing social pathways among network members.³⁷ This Type III intervention represents a class of network interventions that have been found to be effective in HIV prevention (i.e., CDC's EBI—Social Network Strategy).³⁸ Past research has shown that individuals who are members of the same social network are more likely to have similar HIV risk potential.³⁹ SNS identifies HIV positive individuals and/or individuals at risk for acquiring HIV and motivates them to recruit persons from their social network for testing and provides modest compensation for referrals. In so doing, the reach of the testing program increases as does the volume of people tested. In a recent study conducted by members of C3,⁴⁰ the social network strategy (SNS)

was superior in HIV case identification when compared to standard testing approaches, such as those in health care settings (i.e. emergency department) or contact tracing. These findings are not surprising given that social network theory, such as homophily (i.e. birds of a feather)⁴¹ suggest that subsequent waves of referred network members will resemble an index client's attributes.

STUDY DESIGN

The scientific premise of C3 is to engage disenfranchised people in COVID-19 testing and vaccination referral through social network referral combined with theory-driven COVID-19 prevention messaging. Eligible CJI and Latinx clients (and the overlap between the two) will be enrolled into C3.

Using a two-arm randomized controlled trial design, participants will be enrolled into the SNS arm (involves social networking referrals only) or the SNS+messaging arm. The latter includes affirmation/misinformation correction messaging (discussion tools and coaching). SNS and SNS+messaging arms will both include an initial group of index study participants who will refer their network members into the study and the process will repeat itself one more time for a total of 3 waves.

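### Both SNS and SNS+ are hypothesized to outdo contact tracing, but only SNS has a planned comparison, and randomized days do not guarantee that its first comparator group is similar

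*Combined protocol and SAP*

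**What the plan says.** **Hypothesis (Methods, Aim):** "We also hypothesize that both SNS and SNS+ will generate more people tested per index as compared to COVID-19 contact tracing". The aim itself speaks of SNS strategies in the plural.

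**Arms (Study Design):** "participants will be enrolled into the SNS arm (involves social networking referrals only) or the SNS+messaging arm". Under Study Visit Procedures, the description of the messaging arm adds: "The SNS+ condition will include everything described in the SNS condition above". SNS and SNS+ are thus two separately named conditions, the second being the first plus messaging.

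**Planned comparison (Secondary outcome analyses):** a negative binomial regression of referrals tested per index client, between C3 recruits "assigned to the SNS condition and a comparison group of clients at the same sites receiving standard contact tracing only". It is run twice:

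- First, with only "those contact tracing clients who visited the sites on a day randomized to no C3 recruitment". The reason given is "since these individuals should, on average, be similar to those recruited into the study".
- Then with a larger set of non-study clients, of which the plan says "this will use covariates capturing demographic and other client characteristics to adjust for potential differences". This version again names only the SNS group on the C3 side.

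The paragraph closes: "Analyses will use generalized linear mixed models similar to those described above, as appropriate".

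**The concern.** There are two linked problems, both confined to the contact-tracing comparison.

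First, the hypothesis names two arms and the analysis names one. If the plan is followed as written, half of a stated hypothesis reaches the report without a test. Any SNS+ contrast with contact tracing would then be added after the fact.

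Second, the first comparison is presented as close to like-with-like on the strength of randomized days. Selection into C3 acts on one side only, and the plan does not clearly commit this comparison to covariate adjustment. A reader could take the result as having more causal weight than the design gives it.

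**Working it through.** The documents give no sample size, effect size or power for the contact-tracing comparison, so there is no plan figure to reproduce. The stated 87% power concerns SNS versus SNS+.

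**Step 1. Contrasts hypothesized and planned.**

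| Contrast with contact tracing | Hypothesized (Methods) | Planned (Secondary outcome analyses) |
|---|---|---|
| SNS | yes | yes, twice |
| SNS+ | yes | no |

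Reading SNS in the analysis as covering both arms does not work. The primary analysis paragraph, just before it, uses the same label for one arm set against the other.

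**Step 2. Can the randomized result stand in?** On the log scale, SNS+ versus contact tracing equals (SNS+ versus SNS) plus (SNS versus contact tracing). That sum answers the hypothesis only if both terms refer to indexes. The primary analysis includes all enrolled participants. From the Study Design section:

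- index share: 300 / 2,400 = 12.5%;
- network referral share: 2,100 / 2,400 = 87.5%.

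The Methods section puts indexes at 12%, that is 0.12 × 2,400 = 288, which changes little. With equal allocation, about 300 / 2 = 150 indexes (or 144) fall in SNS+ and enter no planned comparison with contact tracing.

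**Step 3. What randomized days balance.** They make all attendees on recruitment days comparable, on average, with all attendees on no-recruitment days. The planned comparison instead sets a selected subset of one side against contact-tracing clients of the other:

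- C3 indexes must meet the index criteria, have no active symptoms, not be on parole, and consent (Inclusion and exclusion criteria; Informed Consent).
- Some may be reached through social media or lists from previous studies (recruitment activities), which no site visit day governs.
- No matching restriction is stated for the comparators.

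The mechanism can be illustrated, but every rate here is an assumption. Suppose SNS has no effect, a share p of clients is willing to join, and willing clients have k times the referral yield of the others. The recruited-to-comparator ratio is then k / (p·k + 1 − p):

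- k = 1: 1.00;
- k = 1.25, p = 0.5: 1.25 / 1.125 = 1.11;
- k = 1.5, p = 0.5: 1.5 / 1.25 = 1.20;
- k = 1.5, p = 0.3: 1.5 / 1.15 = 1.30;
- k = 2, p = 0.5: 2 / 1.5 = 1.33.

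Suppose also that half of clients are eligible and that eligible clients have 0.8 times the yield of the others. With k = 1.25 and p = 0.5, the ratio is (0.8 × 1.25) / (0.9 × 1.125) = 0.99. With no willingness effect it is 0.8 / 0.9 = 0.89. The bias can therefore be absent, upward, downward or self-cancelling. Comparing all attendees by type of day gives 1.00 in every case.

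**Step 4. Adjustment.** Adjustment for group differences is attached to the larger comparison. The closing sentence refers back to models whose primary version starts unadjusted, relying on the randomization, and then adds covariates. Whether that sequence applies to the first contact-tracing comparison is left open.

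**The case against.** - **The arms are nested.** SNS+ contains all of SNS, so SNS against contact tracing plus the randomized contrast gives some evidence on SNS+. This stands, but it is indirect, draws mostly on referrals, and is not a planned test.
- **Narrowing the hypothesis to SNS would also remove the mismatch.** True, but it gives up a question that the plan states and that data already being collected can address.
- **The groups may be close.** Comparators come from the same sites, most of which list CJI or Latinx populations in Table 1. The index criteria are also broad, since having witnessed a negative police encounter is enough. This narrows the gap. It does not remove selection by symptoms, parole status or consent.
- **The plan's wording is hedged, and randomized days do provide something.** Both points stand. The similarity sentence needs qualifying rather than removing.
- **Adjustment may be intended.** The closing sentence can fairly be read as carrying over the primary sequence of unadjusted and then adjusted models. It does not commit to that, so this is an ambiguity to settle.
- **Appendix A is not supplied.** It holds site-specific recruitment and conduct details and may say how randomized days operate. The supplied text says nothing more about them.

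**Conclusion.** The concern holds. One of two hypothesized contrasts with contact tracing has no planned test; this rests on the text alone. For the SNS comparison that is planned, day randomization does not guarantee similar groups, and covariate adjustment is explicit only for the larger version.

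A reader might infer more, and the documents do not support it:

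- **That the first comparison is biased, or biased in favour of SNS.** Nothing supplied gives the size or direction of any difference. The ratios above show only a mechanism under assumed rates, and some of them are at or below 1.
- **That the first comparison will be left unadjusted.** The plan is unclear here; it does not rule adjustment out.
- **That the trial's main result is compromised.** The randomized SNS versus SNS+ comparison does not depend on contact-tracing clients.

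This should be corrected before analysis, but its reach is limited to a secondary analysis.

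**What to change.** 1. In the planned negative binomial model, use a group term with three categories (contact tracing, SNS, SNS+) and report both contrasts with contact tracing. If the claim is that both succeed, as the hypothesis is worded, no multiplicity adjustment is needed. If each is to be claimed separately, say so and use an adjustment such as Holm.
2. Apply to the first comparison the covariate adjustment already planned for the larger one, and state this explicitly.
3. Qualify the similarity sentence to say that day randomization balances site attendees only, and report the comparison as non-randomized.

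Restricting comparators to the C3 index criteria should be at most a sensitivity analysis, where site data allow, with a statement of which criteria could not be applied. The supplied text does not say that justice history or income is recorded for non-study clients. The symptom exclusion could shrink the group by an unknown amount, and consent selection would remain.

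The cost is one extra contrast and a weaker causal label on a secondary analysis. No new enrolment is needed, and covariates for non-study clients are already part of the plan.
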